1. INTRODUCTION AND PURPOSE

This Statistical Analysis Plan (SAP) provides a comprehensive, prospectively defined description of all planned statistical analyses for the SLdl-HYS Trial. It was written and finalized **before database lock and unblinding** to prevent outcome reporting bias and data-driven analytical decisions.

This SAP should be read in conjunction with the Study Protocol (Version 2.0, January 2025). In the event of any discrepancy between this document and the protocol, **this SAP takes precedence** for all analytical decisions. All deviations from this plan will be documented with explicit justification in the final statistical report.

2. STUDY OVERVIEW

Design: Prospective, randomized, controlled, parallel-group, single-blind trial

Setting: Department of Obstetrics and Gynecology, CHU Hédi Chaker, Sfax, Tunisia (monocentric)

Intervention: Single-layer (SLC) vs. double-layer (DLC) uterine closure after primary cesarean section

Total enrolled: 384 participants (192 per group)

Follow-up: 6–8 weeks and 6–7 months postpartum

Study end date: 30 April 2026

3. PRIMARY AND CO-PRIMARY ENDPOINTS

Endpoint	Time Points	Variable Type
----------	-------------	---------------

Residual Myometrial Thickness (RMT)	6–8 weeks AND 6–7 months	Continuous (mm)
CSD Prevalence (indentation \geq 2 mm, Jordan 2019)	6–8 weeks AND 6–7 months	Binary

4. ANALYSIS POPULATIONS

4.1 Intent-to-Treat (ITT) — PRIMARY

All 384 randomized participants, analyzed as allocated regardless of protocol adherence.

4.2 Per-Protocol (PP) — SENSITIVITY

Participants who:

- Received allocated technique
- Completed 6-month follow-up with valid TVUS
- Had no major protocol deviations

4.3 Safety Population

All participants who underwent the surgical intervention.

5. DESCRIPTIVE STATISTICS

Variable Type	Statistic
Continuous, normal	Mean \pm SD
Continuous, skewed	Median (IQR)
Categorical	n (%)

Normality assessment: Kolmogorov-Smirnov test + Shapiro-Wilk test + Q-Q plots + histograms

No p-values for baseline comparisons (CONSORT 2010 recommendation)

6. PRIMARY OUTCOME STATISTICAL ANALYSIS

6.1 RMT Analysis

Step 1 — Unadjusted:

If normally distributed	Independent t-test (or Welch's t-test)
If non-normal	Mann-Whitney U test

Step 2 — Adjusted (primary analytical approach):

Multiple linear regression with RMT as dependent variable

Covariates: Treatment group, age, BMI, gestational age, uterine exteriorization, surgeon category, labor duration, CS indication

Reported: Adjusted MD, 95% CI, R^2 , adjusted R^2 , F-statistic, model p-value

Assumption verification: Linearity, homoscedasticity (Breusch-Pagan), independence (Durbin-Watson), multicollinearity ($VIF < 5$), normality of residuals (Shapiro-Wilk)

6.2 CSD Prevalence Analysis

Unadjusted: Chi-square or Fisher's exact test → RR, ARR, NNT/NNH with 95% CI

Adjusted: Binary logistic regression at 6–8 weeks and 6–7 months

- Variables: $p < 0.20$ in univariate + a priori confounders
- Fit: Hosmer-Lemeshow test
- Multicollinearity: VIF
- Discrimination: AUC (ROC curve)
- Results: Adjusted OR with 95% CI

7. SECONDARY OUTCOME ANALYSES

7.1 Repeated Measures — Linear Mixed-Effects Model (LME)

Fixed effects: Treatment, time (6w vs. 6m), treatment × time interaction

Random effect: Participant intercept

Covariance: Unstructured (preferred); compound symmetry if needed

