- Independence of residuals (Durbin-Watson test)

- Absence of multicollinearity (Variance Inflation Factor < 5)
- Normality of residuals (Shapiro-Wilk on residuals)

Reported: Adjusted MD (β coefficient) with 95% CI, R^2 , adjusted R^2 , F-statistic, overall model p-value

SAP-4.3 CSD Prevalence — Analysis

Unadjusted:

- Chi-square test or Fisher's exact test (if expected cell count < 5)
- Relative Risk (RR) with 95% CI
- Absolute Risk Reduction (ARR) and Number Needed to Treat/Harm (NNT/NNH)

Adjusted:

- **Binary logistic regression** at 6–8 weeks and at 6–7 months
- Covariates: same set as RMT regression model
- Variables with $p < 0.20$ in univariate analysis AND a priori confounders (age, parity, BMI, indication) included
- Model fit: **Hosmer-Lemeshow test**
- Multicollinearity: **Variance Inflation Factors (VIF)**
- Discrimination: **Area Under the ROC Curve (AUC)**
- Results expressed as adjusted **Odds Ratios (OR)** with 95% CI

SAP-5. SECONDARY OUTCOME ANALYSES

SAP-5.1 Continuous Secondary Outcomes

- Unadjusted: t-test or Mann-Whitney U as appropriate
- Adjusted: Multiple linear regression (same covariate set)
- Results: Mean difference or median difference with 95% CI

SAP-5.2 Binary Secondary Outcomes (Complications, Transfusion)

- Unadjusted: Chi-square or Fisher's exact test
- Results: RR, ARR, NNT/NNH with 95% CI

SAP-5.3 CSD Morphological Dimensions

Analyzed within the **CSD-positive subgroup only**:

- Depth, length, width: Mann-Whitney U test
- **CSD Volume** (ellipsoid formula): Mann-Whitney U test

SAP-5.4 Repeated Measures — RMT at 6 Weeks and 6 Months

Method: Linear Mixed-Effects Model (LME)

Model structure:

- Fixed effects: treatment group, time point (6 weeks vs. 6 months), treatment × time interaction
- Random effect: participant-level intercept (accounts for within-subject correlation)
- Covariance structure: Unstructured (preferred); compound symmetry if convergence issues

Interpretation:

- Significant interaction ($p < 0.05$): treatment effect differs across time points
- Non-significant interaction: main effects interpreted independently

SAP-5.5 Symptom Outcomes (Ordinal / Binary)

- Binary symptoms (spotting, dyspareunia): Chi-square or Fisher's exact test; RR with 95% CI
- **Paired temporal evolution** (6 weeks → 6 months within each group): **McNemar's test**
- Adjusted: Binary logistic regression

SAP-5.6 Hemoglobin Variation and Blood Loss

- ΔHb : t-test or Mann-Whitney U; mean difference with 95% CI

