11. SAMPLE SIZE CALCULATION

The sample size was determined based on the primary outcome — **RMT at 6 months** — using the standard formula for comparison of two independent means:

$$n = \frac{2 \times (Z_{\alpha/2} + Z_{\beta})^2 \times \sigma^2}{\Delta^2}$$

Parameters:

- Two-sided significance level: $\alpha = 0.05$ ($Z_{\alpha/2} = 1.96$)
- Statistical power: 80% ($Z_{\beta} = 0.842$)
- Conservative standard deviation: **$\sigma = 3.5$ mm**
- Minimum clinically meaningful difference: **$\Delta = 1.3$ mm**

Base sample size: 114 participants per group

Adjustment for loss to follow-up:

Based on local postpartum follow-up data and published literature, a **30% loss to follow-up rate** was anticipated:

$$n_{adjusted} = \frac{114}{1 - 0.30} \approx 163 \text{ per group}$$

Total enrolled: 384 participants (192 per group)

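### The repeated-measures RMT model leaves out the baseline covariates of the primary regression; adding those fixed before allocation would give a modest, nearly free precision gain

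*Combined protocol and SAP*

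**What the plan says.** The combined document (SAP part, section 7.1) specifies the mixed model by "Fixed effects: Treatment, time (6w vs. 6m), treatment × time interaction". The standalone SAP (SAP-5.4) gives the same three terms: "Fixed effects: treatment group, time point (6 weeks vs. 6 months), treatment × time interaction". Each adds a participant intercept, described in SAP-5.4 as "Random effect: participant-level intercept (accounts for within-subject correlation". Neither section names a baseline covariate.

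The primary RMT analysis is different. Section 6.1 of the combined document labels it "Step 2 — Adjusted (primary analytical approach" and lists "Covariates: Treatment group, age, BMI, gestational age, uterine exteriorization, surgeon category, labor duration, CS indication". SAP-4.2 has the same list, with RMT at 6–7 months as its only dependent variable. For continuous secondary outcomes in general, SAP-5.1 plans "Adjusted: Multiple linear regression (same covariate set". SAP-5.4 does not carry that rule over and gives no reason for dropping it.

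The protocol's sample size section anticipates a "30% loss to follow-up rate". Missing RMT at 6 months is also addressed outside the mixed model, by the five imputation scenarios (SA-3), inverse probability weighting (SA-4) and a complete-case comparison (SA-6).

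**The concern.** The primary objective asks about RMT at both visits and about whether the effect is stable over time. The mixed model is the one specified model that takes the two visits together. In the standalone SAP no other model gives an adjusted RMT effect at 6–8 weeks. Leaving out covariates that the plan adjusts for elsewhere has two possible consequences.

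- **Precision.** RMT variation that the covariates could explain stays in the residual, so the interval for the treatment effect at each visit is wider than necessary.
- **Missing data.** A likelihood-based mixed model is unbiased when loss is random given what the model contains. Here that is arm, visit and the RMT values observed. If loss also depends on a prognostic covariate, and does so differently in the two arms, the estimated effect shifts.

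The mixed model and the primary regression would also give 6-month effects that differ in their covariates, as well as in how they use women with only one scan.

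**Working it through.** **Inputs.** From the protocol's sample size section: SD 3.5 mm, difference 1.3 mm, two-sided α 0.05, power 80%, 30% loss, 192 enrolled per group. Not in the documents, and therefore assumed: the share R² of RMT variance that the covariates explain (0.05 to 0.30), and the correlation ρ of RMT between visits given the covariates (0.5 and 0.7).

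**1. The plan's own figure.** n = 2 × (1.96 + 0.842)² × 3.5² / 1.3² = 113.8, so 114 per group. 114 / 0.70 = 162.9, so 163. Both match the protocol. Expected evaluable at 6 months: 192 × 0.70 = 134 per group.

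**2. Precision at one visit.** Adjustment multiplies the SD by √(1 − R²). Without it, SE = 3.5 × √(2/134) = 0.428 mm and the 95% CI half-width is 1.96 × 0.428 = 0.838 mm.

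| R² (assumed) | SE ratio | CI half-width, mm | Power for 1.3 mm |
|---|---|---|---|
| 0 | 1.000 | 0.838 | 86.0% |
| 0.05 | 0.975 | 0.817 | 87.7% |
| 0.10 | 0.949 | 0.795 | 89.3% |
| 0.20 | 0.894 | 0.750 | 92.5% |

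Power is shown only for scale, since the mixed model is not the powered analysis.

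**3. The same for the 6-month effect in the mixed model.** Here the 6-week scan already carries part of the covariate information, so the gain is slightly smaller. Suppose every woman has the 6-week scan and 70% have the 6-month scan. The variance of the 6-month effect is then proportional to (SD²)[c² + (1 − c²)/0.70], where c is the between-visit correlation in the model fitted. Without covariates c = R² + (1 − R²)ρ and the SD is 3.5. With them c = ρ and the SD is 3.5√(1 − R²). For R² = 0.20 and ρ = 0.5:

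- without: c = 0.60, SE = 3.5 × √[(2/192) × (0.36 + 0.64/0.70)] = 0.403
- with: SE = 3.130 × √[(2/192) × (0.25 + 0.75/0.70)] = 0.367, ratio 0.911

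The ratios for R² 0.05 and 0.10 are 0.979 and 0.957. So at 6 months the reduction is about 2%, 4% and 9%, against 2.5%, 5.1% and 10.6% from step 2.

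**4. Interaction.** In a simulation of 384 women with about 30% lost by 6 months (R² 0.20, ρ 0.5), the SE of treatment × time was 0.370 without the covariate and 0.367 with it. A covariate that acts alike at both visits largely cancels from a within-woman change.

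**5. Bias from loss.** When loss depended on the covariate in the same way in both arms, the simulated bias was at most 0.024 mm with or without adjustment, which is simulation error.

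Now take a two-level covariate with a 50:50 split, and loss of 30% ± 15 points that runs in opposite directions in the two arms (45% against 15% within a level). The covariate means of the women retained then differ between arms by 2 × 0.15/0.70 = 0.429, with levels coded ±1. Each unit is worth 3.5√R² mm, and the 6-week scan absorbs a fraction c of it. Bias ≈ 0.429 × 3.5√R² × (1 − c):

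| R² | ρ = 0.5 | ρ = 0.7 |
|---|---|---|
| 0.05 | 0.16 mm | 0.10 mm |
| 0.10 | 0.21 mm | 0.13 mm |
| 0.20 | 0.27 mm | 0.16 mm |
| 0.30 | 0.29 mm | 0.17 mm |

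Simulation under opposite-direction loss gave 0.09–0.30 mm, or 7–23% of 1.3 mm. With the covariate in the model the bias fell to about 0.02 mm or less. Under this pattern the interaction was shifted by a similar amount.

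**The case against.** An unadjusted mixed model is a legitimate secondary analysis in a 1:1 randomised trial, and the SAP interprets the interaction first, where covariates add almost no precision. The adjusted 6-month effect already comes from the primary regression. All of this stands, and it is why the point is minor.

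Four stronger readings are tempting, and the documents do not support them.

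- **That the model ignores known predictors of RMT.** Identifying predictors is secondary objective 6, and no R² is given. What can be said is that the plan adjusts for these covariates elsewhere.
- **That the trial's handling of the 30% loss rests on this model, or that only this model keeps women with one scan.** SA-3 includes last-observation and 6-week carry-forward scenarios, SA-4 weights for loss, and the 6–8-week comparison uses those women too.
- **That the effect is materially biased.** This needs loss that depends on a covariate in opposite directions by arm. The documents suggest no such mechanism, and blinding of participants (section 7.3) makes it less likely. Placing half the loss before the 6-week scan as well can raise the figure to 0.47 mm, but only by adding another assumption.
- **That a disagreement with the primary result could not be interpreted.** SAP-4.1 reports the unadjusted difference and SA-6 a complete-case result, so the effect of covariates and the effect of using partial follow-up can be separated.

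**Conclusion.** The omission is real in both SAPs, and it departs without explanation from the adjustment used in the primary regression and in SAP-5.1. The mixed model remains valid. What is lost is precision in the visit-specific treatment effects: about 2%, 5% or 11% of the SE for an assumed R² of 5%, 10% or 20%, and slightly less at 6 months. Almost nothing is lost for the interaction. Bias of about 0.1–0.3 mm appears only under a deliberately strong assumption of arm-differential, covariate-dependent loss; otherwise the gain is precision only. Severity is low. The primary conclusion does not depend on this model.

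**What to change.** In SAP-5.4 and in section 7.1 of the combined document, add to the fixed effects the primary-model covariates that are fixed before allocation: age, BMI, gestational age, surgeon category and indication, each with its interaction with time. State that the adjusted treatment difference with 95% CI will be reported at each visit. Leave out uterine exteriorization, which is at the surgeon's discretion and not clearly settled before allocation is revealed, and labor duration, which SAP-4.2 includes only where applicable.

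The cost is one line in each SAP and no new data. With indication in the three categories of the subgroup tables, there are 4 + 2 = 6 covariate terms, or 12 with time. With 384 women and 30% loss by 6 months, the scans number between 2 × 269 = 538 and 384 + 269 = 653. The change should be written before unblinding, or recorded as a deviation as both SAPs require.

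This does not help women with no scan, who add nothing to the mixed model with or without covariates. They are addressed by the planned imputation and weighting, whose variables are not listed and could usefully be named in the same revision.

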7.2 Intraoperative Continuous Outcomes

PSTC formula:

$$PSTC = \frac{VST \times (Hct_{preop} - Hct_{D1})}{35} \times 100 + (n_{RBC} \times 500)$$

VST = Pre-pregnancy weight \times 65 \times 1.4

Analysis: Mann-Whitney U; median difference with 95% CI

7.3 Binary Outcomes

Chi-square / Fisher's exact; RR, ARR, NNT with 95% CI

7.4 Paired Temporal Symptom Evolution

McNemar's test (within-group: 6 weeks \rightarrow 6 months)

7.5 CSD Volume

Formula: $V \text{ (mm}^3\text{)} = (\pi/6) \times \text{Length} \times \text{Width} \times \text{Depth}$

Analysis: Mann-Whitney U (in CSD-positive subgroup only)

8. ADVANCED ANALYSES

8.1 Clinical Predictive Model

Method: Firth penalized logistic regression (justified by Peduzzi events/variable threshold)

Validation: Bootstrap (10,000 replications) + 10-fold cross-validation + 70/30 split

Threshold: Youden Index

Performance: AUC, sensitivity, specificity, PPV, NPV

8.2 Mediation Analysis

Framework: Imai et al. counterfactual approach

Mediator: CSD at 6–8 weeks

Outcome: RMT at 6–7 months

Estimated quantities: ACME, ADE, total effect, proportion mediated

Inference: Bootstrap (10,000 replications)

Sensitivity: Critical p analysis

8.3 Inter-Operator Homogeneity

Breslow-Day test for consistency of treatment effects across surgeons

8.4 Measurement Reproducibility (n = 30 double-blind readings)

Variable	Method
RMT, AMT (continuous)	Intraclass Correlation Coefficient (ICC)

Variable	Method
CSD presence (categorical)	Cohen's Kappa
Temporal concordance (6w vs. 6m)	Lin's Concordance Correlation + Bland-Altman analysis

9. SUBGROUP ANALYSES (EXPLORATORY)

Factor	Categories	Test
BMI	< 30 vs. 30–34.9 kg/m ²	Interaction term (LRT)
Gestational age	37–38+6 vs. ≥ 39 weeks	Interaction term (LRT)
CS type	Scheduled vs. Intrapartum	Interaction term (LRT)
CS indication	Dystocia / Fetal / Maternal	Interaction term (LRT)
Uterine exteriorization	Yes vs. No	Interaction term (LRT)
Surgeon category	Senior vs. Resident	Interaction term (LRT)

Results presented in **forest plots**. Exploratory only — no conclusions drawn from subgroup results alone.

10. SENSITIVITY ANALYSES

SA	Method
SA-1	Per-Protocol population — repeat primary analysis
SA-2	Exclude major intraoperative complications (corporeal hysterotomy, extension > 2 cm)
SA-3	Five-scenario multiple imputation (MICE): observed data, LOCF, best case, worst case, 6-week status carry-forward
SA-4	Inverse Probability Weighting (IPW) for loss to follow-up
SA-5	RMT threshold analysis: proportion < 2.5 mm and < 3.0 mm (Chi-square)
SA-6	Complete case analysis (for comparison with SA-3)

11. MULTIPLICITY CONTROL

- Primary outcomes: $\alpha = 0.05$, two-sided
- Secondary outcomes: **Holm-Bonferroni correction**
- Unmeasured confounders: **E-value** reported for primary associations

12. MISSING DATA

Little's MCAR test to assess missing data mechanism.

Outcome	Strategy
RMT at 6 months	Five-scenario MICE (SA-3)
Secondary continuous	Complete case + MICE if > 10% missing
Binary outcomes	Complete case
Symptom questionnaires	Full information maximum likelihood (FIML) via mixed models

13. SOFTWARE

Software	Use
SPSS v26.0 (IBM)	Primary analyses
R v4.3 (R Foundation)	LME, mediation, bootstrap, reproducibility, imputation
R packages	lme4, mice, mediation, ggplot2, tableone, pROC, irr, MKmisc

Reproducibility: All R scripts version-controlled and archived. Random seed: `set.seed(2025)`.

14. REPORTING

Results reported per **CONSORT 2010**. Key outputs:

- CONSORT flow diagram
- Table 1: Baseline characteristics (no p-values)

- Table 2: Primary and secondary outcomes
- Table 3: Multivariate analysis (regression models)
- Table 4: Subgroup analysis (forest plots)
- Table 5: Safety summary
- Figure: Bland-Altman plot, ROC curves, forest plots, individual RMT trajectories (6w → 6m)
